9.3.3 Removal of Subjects from Therapy or Assessment

The Investigator may discontinue treating a subject with study treatment or withdraw the subject from the study at any time for safety or administrative reasons. The subject may decide to discontinue study treatment or withdraw from the study at any time for any reason.

The Investigator will document the reason for discontinuing a subject from treatment or from the study.

The Investigator may discontinue treatment or discontinue a subject from the study for any of the reasons listed below:

- Occurrence of AEs
- Occurrence of pregnancy

- Use of a prohibited concomitant medication or treatment (see [Section 9.4.7.3](#))
- Conditions that, in the opinion of the Investigator, would make the subject's continued participation in the study inadvisable (actual condition must be documented)
- Noncompliance (Investigator must describe)
- Withdrawal of consent (subject asked, but not required to give a reason)
- Other (Investigator must describe)

If the study is terminated by the Sponsor, the Investigator will promptly explain to the subject involved that the study will be discontinued and provide appropriate medical treatment and other necessary measures for the subject.

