9.4.7.3 Prohibited Medication/Therapy

Use of any non-study drug treatment for AK lesions on the treatment area is prohibited until Day 57. AK lesions located outside the treatment area may be treated by lesion-directed treatment only, eg, cryotherapy or biopsy, as determined by the Investigator. A list of prohibited medications follows.

Prohibited drug products and treatments that might influence or mask the effects of treatment until Day 57 include: immunomodulators or immunosuppressive therapies, cytotoxic drugs, interferon/interferon inducers, topical or systemic steroids, 5-FU, ingenol mebutate, imiquimod, diclofenac, topical or systemic retinoids, topical salicylic acid, bichloroacetic acid, trichloroacetic acid, acid-containing therapeutic products, benzoyl peroxide, chemodestruction, medicated/therapeutic topical salves or topical steroids, photodynamic therapy, psoralen plus UVA or UVB therapy, artificial tanner, excessive or prolonged exposure to UV light source.¹³

During the Recurrence Follow-up Period, lesion-directed treatment such as cryotherapy or biopsy, and topical treatment is allowed for treatment of AK lesions emerging in any part of the body. Any lesion in the treatment area that is treated during the Recurrence Follow-up Period will be considered as a recurrence.

Subjects are prohibited from applying any topical products, including but not limited to, lotions, creams, and ointments to the treatment area up until the end of Visit 10 (Day 57), except when those medications are prescribed by the Investigator for the management of local skin reactions. All other routinely used topical products can be used on the treatment area from Day 57 onward, at the discretion of the Investigator.

All subjects should be reminded to avoid direct sun or UV exposure to the treatment area throughout the study. From Day 15 onward, if a subject is unable to avoid direct sun or UV exposure to the treatment area, the Investigator may allow the use of sunblock only.

Subjects have unrestricted use of nonmedicated topical products on areas outside of the treatment area during the study. After Day 57, all routinely used topical products can be used.

Any subjects who start systemic therapies for the treatment of AK will be withdrawn from the study.

Any subjects who start topical therapies for AK on the treatment area will be withdrawn from the study.

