5.2 Study Subjects

5.2.1 Definitions of Analysis Sets

- Per-Protocol Set: the group of protocol-eligible subjects who receive 5 days (Cohort 1) or 3 days (Cohort 2) of study treatment and complete at least one scheduled post-treatment AK lesion evaluation
- Evaluable Set: the group of protocol-eligible subjects who receive 5 days (Cohort 1) or 3 days (Cohort 2) of treatment and complete Day 1 and Day 57 AK lesion evaluations
- Safety Analysis/Full Analysis Set: the group of subjects who receive at least one dose of study treatment
- Recurrence Follow-up Set: the group of subjects who achieve complete clearance at Day 57

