5.4 Activity Analyses

5.4.1 Primary Activity Analyses

The proportion of subjects with 100% clearance of all treated AK lesions at Day 57 will be considered to follow a binomial distribution. Based on the number of subjects who achieved 100% clearance at Day 57, the complete response rate and its corresponding 95% Clopper-Pearson Exact CI will be estimated in the Evaluable Set.

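### No scoring rule covers lesion-directed treatment inside the treatment area before Day 57, so a subject cleared that way counts as a complete responder

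*Protocol*

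**What the plan says.** **Prohibition.** Protocol v3.0, 9.4.7.3: "Use of any non-study drug treatment for AK lesions on the treatment area is prohibited until Day 57". Lesion-directed treatment is permitted in that period only outside the area.

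**Mandatory withdrawal.** The same section names two classes: "Any subjects who start systemic therapies for the treatment of AK will be withdrawn from the study" and "Any subjects who start topical therapies for AK on the treatment area will be withdrawn from the study". It names no others.

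**Discretionary removal.** Protocol 9.3.3: "The Investigator may discontinue treatment or discontinue a subject from the study for any of the reasons listed below". The list includes "Use of a prohibited concomitant medication or treatment", with a cross-reference to 9.4.7.3.

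**Analysis.** SAP 5.4.1 works as follows: "Based on the number of subjects who achieved 100% clearance at Day 57, the complete response rate" and its Clopper-Pearson 95% interval are estimated in the Evaluable Set. SAP 5.2.1 requires of that set that subjects be protocol-eligible, receive all 5 or 3 days of treatment, and "complete Day 1 and Day 57 AK lesion evaluations". SAP 5.4.3 treats partial clearance in the same way. SAP 5.2.3 lists protocol deviations and attaches no analysis consequence to them.

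**After Day 57.** Protocol 9.4.7.3 does give a scoring convention for this later period: "Any lesion in the treatment area that is treated during the Recurrence Follow-up Period will be considered as a recurrence".

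**The concern.** The primary endpoint is meant to measure clearance by the study ointment. If a lesion inside the 25 cm² area is frozen or cut out before Day 57 and the subject stays in the study, the Day 57 count can be zero for a reason unrelated to the ointment. The count itself will not reveal this, because Protocol 9.5.1.3.1 tells the Investigator to make it without reference to any other evaluation. Nothing in the SAP then reclassifies the subject.

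Such treatment is banned, but it is not far-fetched. Cryotherapy of AKs outside the area is allowed during the same weeks, the area is small, and a lesion touching its border counts as inside. Protocol 9.4.7.3 also closes by contemplating a decision to give a prohibited treatment.

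At stake is an upward bias in the complete response rate. It would carry through to partial clearance and to the Recurrence Follow-up Set, which consists of subjects with complete clearance at Day 57.

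**Working it through.** **Step 1. Follow a subject through the rules, by type of in-area treatment before Day 57.**

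| Treatment | Withdrawal | If a Day 57 count of zero exists |
|---|---|---|
| Systemic AK therapy | Mandatory (9.4.7.3) | No scoring rule; withdrawal should normally prevent the count |
| Topical AK therapy on the area | Mandatory (9.4.7.3) | As above |
| Lesion-directed or procedural, in the area | At the Investigator's discretion (9.3.3) | Complete responder under SAP 5.2.1 and 5.4.1 |

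The gap is therefore the third row. A residue remains in the first two. A withdrawn subject with no Day 57 count leaves the Evaluable Set and is not scored as a failure. Visit 10 also doubles as the Early Termination visit (Protocol Tables 1 and 2). The SAP gives no analysis window for Day 57, so it does not say whether an early-termination count could stand in.

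**Step 2. Reproduce the plan's own figure.** Inputs from SAP section 4: n=60, 20% against 35%, two-sided alpha 0.05, power 80%. Normal approximation with the null variance under the null hypothesis:

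Φ[(√60 × 0.15 − 1.96 × √(0.20 × 0.80)) / √(0.35 × 0.65)] = Φ[(1.162 − 0.784) / 0.477] = Φ(0.792) = 78.6%

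This is close to the stated 80%. The exact binomial rule (at least 19 of 60) gives 74.8%. The point made here does not depend on that difference.

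**Step 3. Size per case.** 1/60 = 1.67 percentage points. This applies to a subject who has no lesions at Day 57 and would not have cleared on study drug alone.

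**Step 4. Effect on the interval.** The planned rate of 35% is 21/60. Let k be the number of such subjects among the 21. The documents give no value for k, so 0 to 3 is an assumed range. The lower Clopper-Pearson limit is the 2.5% quantile of Beta(x, n − x + 1).

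| k | Scored as non-responders | Rate | Lower 95% limit |
|---|---|---|---|
| 0 | 21/60 | 35.0% | 23.1% |
| 1 | 20/60 | 33.3% | 21.7% |
| 2 | 19/60 | 31.7% | 20.3% |
| 3 | 18/60 | 30.0% | 18.8% |

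If the three were excluded instead, the result would be 18/57 = 31.6% with a lower limit of 19.9%.

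**The case against.** **The protocol already deals with this by withdrawal.** This stands in part. A reader might infer that withdrawal is optional for any competing AK therapy. It is not: 9.4.7.3 makes it mandatory for systemic AK therapy and for topical AK therapy on the area. Only lesion-directed or procedural treatment is left to discretion.

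**The pre- and post-Day-57 periods are not comparable.** This also stands. One might say that the protocol applies opposite rules before and after Day 57. The documents do not support that. Before Day 57 in-area treatment is a deviation, and the plan is silent on how to score it. Afterwards such treatment is allowed, so a convention was needed. The later rule shows what the protocol regards as a sensible score; it is not a contradiction.

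**The term protocol-eligible could be used to remove such a subject.** It could, since SAP 5.2.6.1 applies it after enrolment. But it is undefined. The one recorded use keeps subjects who received 500 mg per daily dose and subjects with a missing dose amount. Exclusion is therefore not assured.

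**The size is small and nothing is decided on it.** Largely right. SAP 5.4.1 estimates a rate and interval and sets no success test; the 20% bound appears only in the sample size rationale. The inference that one case could overturn the result is too strong. One case moves the lower limit across 20% only at exactly 19/60, and there is no formal decision to overturn.

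**Cases would be visible in the listings.** True of deviations, concomitant medications and procedures. No listing changes the response classification.

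**Conclusion.** The point holds in a limited form. For a subject who receives lesion-directed or procedural AK treatment inside the area before Day 57 and is not withdrawn, the stated counting rule credits any resulting clearance to the study drug. The direction is known: removing lesions by other means can only help a subject reach zero.

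The size is 1.7 points per affected subject at n=60, provided that subject would not have cleared on the ointment alone. From the planned 21/60, three such subjects would bring the lower limit below 20%. Both statements assume 60 evaluable subjects and the planned 35% rate.

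The documents neither show nor suggest that any case occurred, and the true number may be zero. In an uncontrolled Phase 2a estimation study this is a worthwhile, inexpensive clarification. It is not evidence that the reported rate is wrong.

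**What to change.** 1. Add to SAP 5.4.1 and 5.4.3: an Evaluable Set subject who receives any non-study AK treatment on the treatment area between Day 1 and the Day 57 count is a non-responder and stays in the denominator. State that products prescribed by the Investigator for local skin reactions are not AK treatment for this purpose.
2. Identify these subjects from the concomitant medication, procedure and deviation records. SAP 5.2.5.2 does not say whether procedure records show location relative to the treatment area, so unclear cases would need to be checked with the site.
3. If subjects withdrawn for such treatment without a Day 57 count are also to be scored as non-responders, amend the Evaluable Set definition in SAP 5.2.1 to keep them. The sentence in item 1 does not reach them.
4. Separately, reconcile Protocol 9.3.3 (discretionary) with 9.4.7.3 (mandatory for two classes). Which withdrawal rule should apply is for the sponsor to decide.

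The cost is a short SAP addition and a review of data already collected, plus a change to the set definition if item 3 is adopted. The rule is conservative: a subject who would have cleared on study drug anyway is scored as a failure, so the response rate may come out slightly lower. With no cases, the estimate does not change.

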9.4 Treatments

The investigational product in the study is KX2-391 Ointment 1%.

9.4.1 Treatment Administered

Information regarding study treatment is provided in [Table 3](#).

[figure not shown]
Table 3 Treatment Administered in KX01-AK-002

Investigational Product	Strength	Size of Treatment Area	Quantity study medication/ KX2-391	Number Applications and Frequency	Study Days Administered
KX2-391 Ointment 1%	1%	25 cm ²	50 mg of study drug = 0.5 mg of KX2-391	1 application daily for 5 consecutive days (Cohort 1) or 3 consecutive days (Cohort 2)	Days 1-5 (Cohort 1) Days 1-3 (Cohort 2)

9.4.2 Identity of Investigational Products

9.4.2.1 Chemical Name and Structural Formula of KX2-391

- Study drug code: KX2-391 Ointment 1%
- Drug Product: KX2-391 free base ointment formulated with glyceryl monostearate and propylene glycol
- Chemical name: *N*-benzyl-2-(5-(4-(2-morpholinoethoxy)phenyl)pyridin-2-yl)acetamide
- Molecular formula: C₂₆H₂₉N₃O₃
- Molecular weight: 431.53 g/mole
- Structural formula:

9.4.2.2 Labeling for Study Drug

Investigational product will be packaged and labeled in a manner consistent with the study and will be designed by:

Kinex Pharmaceuticals, Inc.
[name]
[name]
[name]

Labels will be nonremovable in nature.

Labels for the investigational product will be in accordance with US regulations and will include (but will not be limited to) the following information:

- For clinical study use only
- Name and address of the Sponsor
- Chemical name/drug identifier
- Lot number/batch number
- Storage conditions, expiration date if necessary

9.4.2.3 Storage Conditions

Study drug will be stored in accordance with labeled storage conditions. Temperature monitoring is required at the storage location to ensure that the study drug is maintained within an established temperature range. The Investigator is responsible for ensuring that the temperature is monitored throughout the total duration of the trial and that records are maintained; the temperature should be monitored continuously by using either an in house validated data acquisition system, a mechanical recording device, such as a calibrated chart recorder, or by manual means, such that minimum and maximum thermometric values over a specific time period can be recorded and retrieved as required.

9.4.2.4 Administration of Investigational Products

The study medication is for external topical use on the treatment area. An investigational center staff member will perform the study medication applications. The staff member must wash her/his hands before and after each study medication application.

50 mg of KX2-391 Ointment 1% will be applied topically to a 25 cm² treatment area. This amount contains a total of 0.5 mg KX2-391 free base. KX2-391 Ointment 1% will be applied once daily for 5 consecutive days (Cohort 1) or 3 consecutive days (Cohort 2) (see [Table 3](#)).

The staff member will weigh the appropriate amount of study medication into a weighing boat (or equivalent) using a calibrated scale. The amount of study medication applied will be calculated by determining the difference of the weight of the weighing boat with study medication before and after application. The amount of study medication weighed will be as close to the intended dose as possible.

A study staff member will perform and document a scale accuracy check at least every day before weighing study medication.

KX2-391 Ointment 1% will be applied to the subject's treatment area using a fingertip protected with a powder-free finger cot or examination glove. The study medication will be gently and evenly rubbed over the treatment area, including its borders, until no visible accumulation is evident. The time when the study medication application is completed (Application Completion Time) will be recorded.

The study medication should remain on the treatment area. Subjects must avoid touching or wetting the treatment area for at least 12 hours from time of last application and are not allowed to apply any topical products to the treatment area (see [Section 9.4.7.3](#)). Instructions will be sent home with the subject clarifying on how to care for the treatment area.

9.4.3 Method of Assigning Subjects to Treatment Groups

This is an open-label study with 2 sequential cohorts. Each site will enroll subjects for Cohort 1 (5-day regimen) first, and will not assign any subjects to Cohort 2 (3-day regimen) until being notified. The Sponsor will review accumulating data on Cohort 1 to decide if, when, and where to start Cohort 2. In addition, the Sponsor study team will monitor the enrollment status closely and ensure that any individual site does not enroll too many subjects.

9.4.4 Selection of Doses in the Study

The dose of 50 mg of KX2-391 Ointment 1% applied to a 25 cm² area on the face or scalp for 5 or 3 consecutive days is based on a previous study using the same dose regimen for the treatment of AK on the forearm (study KX01-AK-01-US). Preliminary data show that this regimen had an acceptable LSR and safety profile, with efficacy outcomes considered to warrant further investigation.

9.4.5 Selection and Timing of Dose for Each Subject

[Section 9.4.2.4](#) provides detailed instructions for administering KX2-391 Ointment 1% in this study. Study medication should be applied at about the same time each day.

9.4.6 Blinding

The study will not be blinded.

9.4.7 Prior and Concomitant Therapy

9.4.7.1 Prior Therapy

All medications (prescription and nonprescription including vitamins and dietary supplements), treatments, and therapies including radiotherapy taken 28 days before Day 1 through the final study visit must be recorded in the case report form/electronic case report form (CRF/eCRF). A complete AK treatment history will be recorded on the AK Treatment History CRF/eCRF (see [Section 9.5.1.2.1](#)).

9.4.7.2 Concomitant Medication/Therapy

Concomitant medication/therapies are any new or existing therapy received by the subject after signing the ICF until discharge from the study.

Any medication (including nonprescription medications) or therapy administered to the subject during the course of the study (starting at the date of informed consent) will be recorded on the Concomitant Medication CRF/eCRF.

Use of sunblock or any topical products in the treatment area allowed by the Investigator will be recorded in the Concomitant Medication CRF/eCRF.

The Investigator will record any AE on the Adverse Events CRF/eCRF for which the concomitant medication/therapy was administered.

Subjects will refrain from receipt of any therapy in accordance with the inclusion/exclusion criteria.

9.4.7.3 Prohibited Medication/Therapy

Use of any non-study drug treatment for AK lesions on the treatment area is prohibited until Day 57. AK lesions located outside the treatment area may be treated by lesion-directed treatment only, eg, cryotherapy or biopsy, as determined by the Investigator. A list of prohibited medications follows.

Prohibited drug products and treatments that might influence or mask the effects of treatment until Day 57 include: immunomodulators or immunosuppressive therapies, cytotoxic drugs, interferon/interferon inducers, topical or systemic steroids, 5-FU, ingenol mebutate, imiquimod, diclofenac, topical or systemic retinoids, topical salicylic acid, bichloroacetic acid, trichloroacetic acid, acid-containing therapeutic products, benzoyl peroxide, chemodestruction, medicated/therapeutic topical salves or topical steroids, photodynamic therapy, psoralen plus UVA or UVB therapy, artificial tanner, excessive or prolonged exposure to UV light source.¹³

During the Recurrence Follow-up Period, lesion-directed treatment such as cryotherapy or biopsy, and topical treatment is allowed for treatment of AK lesions emerging in any part of the body. Any lesion in the treatment area that is treated during the Recurrence Follow-up Period will be considered as a recurrence.

Subjects are prohibited from applying any topical products, including but not limited to, lotions, creams, and ointments to the treatment area up until the end of Visit 10 (Day 57), except when those medications are prescribed by the Investigator for the management of local skin reactions. All other routinely used topical products can be used on the treatment area from Day 57 onward, at the discretion of the Investigator.

All subjects should be reminded to avoid direct sun or UV exposure to the treatment area throughout the study. From Day 15 onward, if a subject is unable to avoid direct sun or UV exposure to the treatment area, the Investigator may allow the use of sunblock only.

Subjects have unrestricted use of nonmedicated topical products on areas outside of the treatment area during the study. After Day 57, all routinely used topical products can be used.

Any subjects who start systemic therapies for the treatment of AK will be withdrawn from the study.

Any subjects who start topical therapies for AK on the treatment area will be withdrawn from the study.

The decision to administer a prohibited medication/treatment is done with the safety of the study subject as the primary consideration.

9.4.8 Prohibitions and Restrictions during Study Period

Except for those diagnosed as having diabetes, subjects must be fasted for laboratory assessments (see [Section 9.5.1.5.3](#)); otherwise there are no food, water, beverage, or physical activity restrictions during the study.

9.4.9 Treatment Compliance

Records of treatment administration for each subject will be kept during the study. The clinical research associates (CRAs) will review treatment administration throughout the course of the study.

9.4.10 Drug Supplies and Accountability

The Investigator and study staff will be responsible for the accountability of all clinical supplies (dispensing, inventory, and record keeping) following the Sponsor's instructions. In this matter, the Investigator and study staff must adhere to GCP guidelines, as well as national requirements.

Under no circumstances will the Investigator allow the study drugs to be used other than as directed by this protocol. Clinical supplies will be dispensed only by an appropriately qualified person and will not be dispensed to any individual who is not enrolled in the study.

An accurate and timely record of the receipt of all clinical supplies and dispensing of study drug to the subject must be maintained. This includes, but is not limited to:

- documentation of receipt of clinical supplies
- study drugs dispensing/return reconciliation log, including amount and date of dispensing
- study drugs accountability log
- all shipping service receipts
- documentation of study drug returned to the Sponsor

All forms will be provided by the Sponsor (or its designee). Any comparable forms that the investigational site wishes to use must be approved by the Sponsor. A copy of the drug accountability record must be provided to the Sponsor at the end of the study.

The supplies and inventory records must be made available, on request, for inspection by the Sponsor (or its designee) or a representative of a health authority. If applicable, all unused study drugs and empty containers, are to be returned to the Investigator by the subject and ultimately to the Sponsor at the conclusion of the study unless provision is made by the Sponsor for destruction of supplies and containers at the investigational site. On completion of drug accountability and reconciliation procedures by investigational site personnel and documentation procedures by Sponsor personnel, study drug that is to be returned to the Sponsor, if necessary must be boxed and sealed and shipped back to the Sponsor following all local regulatory requirements.

The CRA(s) will review drug accountability during monitoring site visits and at the completion of the study.

